#### Part B - MAD

The first MAD cohort (Cohort 4) will be initiated after the safety review of SAD Cohort 2, a recommendation to proceed by the SMC, and approval from the Sponsor.

Patients in the MAD cohorts will be randomized 2:1 to either ANK-700 or PBO. Patients will be stratified based upon their use of fumarate medications at study entry within the interactive response technology system. A total of 12 patients will be enrolled per dose cohort (ANK-700, n = 8; PBO, n = 4). Patients will arrive at the clinic on the morning of dosing and will be monitored in-clinic for 8 hours after completion of their first infusion for assessment of acute safety and PK blood sample collection. A total of 3 doses (1 dose every 3 days) will be

administered in Part B, a regimen that was effective in animal models of multiple sclerosis (MS). Patients will return to the clinic on D22, D43, and at 3, 6, and 12 months for follow-up. In the event that patients are unable to return to the clinic for protocol-specified visits, alternative methods for safety assessments and data collection may be employed to ensure the safety of the patient where appropriate.

Doses planned for evaluation in Part B include 0.3 mg/kg (Cohort 4) and 1.0 mg/kg (Cohort 5). Both Part B cohorts will employ sentinel dosing to monitor for the acute and subacute safety of multiple doses of ANK-700. In this design, the first 2 patients in a cohort (1 ANK-700 and 1 PBO) will complete all 3 doses and then complete an additional 14 days of safety monitoring (through D22) before dosing can be initiated in any further patients.

Cohort 5 will only commence after review of the safety, tolerability, and available PK data of all the SAD cohorts (Cohorts 1 to 3) and Cohort 4, recommendation by the SMC, and approval by the Sponsor.

Please see Table 2 for the complete schedule of assessments for Part B.

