# Study ANK-700-01 in Relapsing-Remitting Multiple Sclerosis

a All patients should be contacted by site staff 1 day before each study visit for assessment of COVID-19 signs and symptoms.

- b Early termination visit only if patient discontinues within 28 days of dosing.
- c On D1 patients will be observed in the clinic/hospital unit for 8h after completion of IV infusion and followed up with by phone following discharge 24 hours after dosing.
- d Pes will also be conducted on study as clinically indicated.
- e Includes weight at screening only.
- f Pregnancy test at screening must be serum; serum or urine tests are acceptable on D1, D4, and D7 prior to dosing. Screening and dosing day pregnancy tests must be negative before study drug is administered. Additional pregnancy monitoring per local guidelines may be implemented.
- g Samples/measurements taken pre-dose.
- h Vital signs include pulse rate, temperature, and diastolic and systolic blood pressure.
- i In the event of a suspected disease relapse, an unscheduled MRI and EDSS assessment may be performed if deemed clinically necessary.
- j The screening MRI must be performed ≥ 10 days prior to dosing on D1. For re-screening, the MRI only needs to be repeated if the previous assessment has been completed >3 months of scheduled dosing or if a relapse has occurred since last assessment
- k The MRI at D22 may be performed up to 3 days before the D22 visit.
-  The MRI at D90 may be performed within 2 weeks of the scheduled D90 visit.
- m On D1, patients will be observed in the clinic for 8 h after completion of IV infusion.
- n On D4 and D7, patients will be observed for 4 h after completion of IV infusion.
- o On D1, 1 PK sample will be taken pre-dose (≥ 5 min prior to infusion), with all subsequent PK samples taken after the end of infusion (EOI) at the following time points: EOI 0 (+2) min, EOI 7 (±2) min, EOI 15 (±2) min, EOI 30 (±5) min, EOI 1 h (±5 min), EOI 2 h (±5 min), EOI 3 h (±5 min), EOI 4 h (±5 min), EOI 6 h (±5 min) and EOI 8 h (±5 min). PK samples to be taken from the arm that did not receive the infusion. The exact date and time of each sample collection must be recorded for all collected samples.

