#### 4.2. PART B – MULTIPLE ASCENDING DOSE

The first MAD cohort (Cohort 4) will be initiated after the safety review of SAD Cohort 2 (Part A), a recommendation to proceed by the SMC, and approval by the Sponsor.

Patients in the MAD part will be randomized 2:1 to either ANK-700 or PBO. Patients will be stratified based upon their use of fumarate at study entry within the interactive response technology (IRT) system. A total of 12 patients will be enrolled per dose cohort (ANK-700, n = 8; PBO, n = 4). Patients will arrive at the clinic on the morning of dosing and will be monitored in-clinic for 8 hours after completion of their first infusion for assessment of acute safety and PK blood sample collection. A follow up phone call 24 hours after dosing will be performed to ensure the patient did not experience any acute safety events after discharge.

- If patients are experiencing active AE(s) which require clinical monitoring at the end of the clinic/hospital unit monitoring period they should not be discharged and followed up per PI assessment
- If feasible, patients should be advised to have someone stay with them after discharge until 24 hours have elapsed after study drug administration on D1.
- If patients do not live within 1-hour travel time of an emergency medical facility, they should remain in the clinic/hospital unit for the first 24 hours after study drug administration.
- Patients should be instructed not to drive themselves to seek emergency medical treatment at any time during the study.

A total of 3 doses (1 dose every 3 days on D1, D4, and D7) will be administered in Part B, a regimen that was effective in animal models of MS. Patients will return to the clinic on D22, D43±2, and at 3, 6, and 12 months for follow-up.

Study ANK-700-01 in Relapsing-Remitting Multiple Sclerosis

[figure not shown]
Doses planned for evaluation in Part B include 0.3 mg/kg (Cohort 4) and 1.0 mg/kg (Cohort 5). Both Part B cohorts will employ sentinel dosing to monitor for the acute and subacute safety of multiple doses of ANK-700. In this design, the first 2 patients in each cohort (1 ANK-700 and 1 PBO) will complete all 3 doses and complete an additional 14 days of safety monitoring (through D21) before initiating dosing for any subsequent patients. Based upon the expected short half-life (< 7 minutes) of ANK-700, no accumulation is anticipated with multiple doses administered 3 days apart.

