After all patients within the first MAD cohort (Cohort 4) have been followed for 21 days, a safety review will be performed by the SMC to review all AEs and available laboratory test and PK data from Cohort 4 and all SAD cohorts. Initiation of Cohort 5 will only commence after review of the safety, tolerability, and available PK data of all the SAD cohorts (Cohorts 1 to 3) and Cohort 4 through D22, recommendation by the SMC, and approval by the Sponsor.

For all patients in Part B, the study will consist of a screening period of up to 28 days, followed by 3 doses of ANK-700, 1 dose administered on D1, D4, and D7. The first dose on D1 will be followed by a 8-hour monitoring period in the clinic/hospital unit; each additional dose will be followed by a 4-hour monitoring period in the clinic/hospital unit. Blood and serum samples will be collected for PK and ADA assessments during Part B of the study. Patients in Part B may be replaced if they do not receive the full 3 doses of study drug or do not complete the D22 visit, as long as the discontinuation was not due to a DLT. In the event that patients are unable to return to the clinic for protocol-specified visits, alternative methods for safety assessments and data collection may be employed to ensure the safety of the patients where appropriate.

Please see Table 2 for the complete schedule of assessments for Part B.

Figure 1: Overview of Study ANK-700-01

**Single Ascending Dose (SAD) (Part A):** 3 patients will be dosed IV with ANK-700 in each cohort. Initiation of the next dose cohort will commence once all patients in a cohort reach D15 and upon acceptable safety review and recommendation by SMC and approval by the Sponsor.

Multiple Ascending Dose (MAD) (Part B): the first MAD cohort (Cohort 4) will be initiated only after acceptable safety review of SAD Cohort 2, recommendation by the SMC, and approval by the Sponsor. Patients are randomized 2:1 to ANK-700 or PBO. Initiation of Cohort 5 will commence once all patients in Cohort 4 reach D22 and upon acceptable safety review of Cohorts 1 to 4, recommendation by the SMC, and approval by the Sponsor.

**Abbreviations**: D = day; IV = intravenously; MAD = multiple ascending dose; PBO = placebo; SAD = single ascending dose; SMC = Safety Monitoring Committee.

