#### **4.6. DOSE-LIMITING TOXICITIES**

Dose-limiting toxicities for Study ANK-700-01 include any Grade 2 AE not resolving within 14 days or any ≥ Grade 3 AE occurring during the dose-escalation safety monitoring period (D1 to D15 in Part A; D1 to D22 in Part B). DLTs do not include those AEs attributable solely to intercurrent illness or other concomitant medications. Any DLT experienced during the dose-escalation safety monitoring period will result in study pause and review by the SMC.

Any  $\geq$  Grade 4 AE will result in notification to the Food and Drug Administration (FDA) in parallel with the SMC; all study dosing and enrollment will be paused pending review by FDA.

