#### 4.7. Dose Escalation Safety Monitoring Period

In Part A, the dose-escalation safety monitoring period is from the beginning of the IV administration of ANK-700 through the D15 clinic visit. Any AEs that meet the criteria defined in Section 4.6 but occur after the dose-escalation safety monitoring period of Part A, may be considered by the SMC in the evaluation for Part B dose selection.

The dose-escalation safety monitoring period in Part B is from the beginning of the first IV administration of ANK-700/PBO through the D22 clinic visit.

The monitoring period is supported by nonclinical animal data, which demonstrate:

- ANK-700 is cleared from circulation in < 7 minutes, ensuring that > 5 half-lives have elapsed during the safety monitoring period
- T-cell tolerance induction can be observed as early as 1 week after drug administration in nonclinical models, ensuring the mechanism of action will be active and robust during the safety monitoring period
- Immunologically active antigen cannot be detected in animals 7 days after GP-peptide administration, ensuring that any processed antigen will be cleared during the safety monitoring period

AEs and any abnormal clinical parameters, including laboratory findings, observed during this period will be used by the SMC to determine whether dose escalation should proceed.

No patient with a DLT will be replaced.

In both parts, patients will be monitored in the clinic for 8 hours after the completion the first IV administration of ANK-700/PBO. In Part B, patients will be monitored in the clinic for 4 hours after completion of their second and third dose.

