#### 4.9. INDIVIDUAL AND COHORT STOPPING RULES

During the dose-escalation safety monitoring period, any DLT will result in a pause in enrollment and a thorough review by the SMC before treating any additional patients. Any ≥ Grade 4 AE will result in notification of the FDA in parallel with the SMC, and study dosing and enrollment will be paused pending review by FDA.

For Part A, if 1 of the first 3 patients experiences a DLT within the safety monitoring period (D1 to D15) in a given cohort, 3 additional patients will be enrolled and evaluated in that cohort before dose escalation can occur if recommended by the SMC and only after consultation with the FDA for any  $\geq$  Grade 4 AE. If 2 or more patients experience a DLT at a given dose level during the dose escalation evaluation period of Part A (D1 to D15), then that dose level will be considered to have exceeded the non-tolerated dose (NTD), and no further escalation will proceed.

If a patient experiences a DLT during the dose-escalation safety monitoring period of Part B, no additional doses will be administered to that patient. If 1 patient experiences a DLT during the dose-escalation safety monitoring period of Part B, the study will be paused to determine if any dose adjustments are needed and/or if the study should dose any additional patients. For any  $\geq$  Grade 4 AE, the study will only continue after consultation with the FDA. If 2 or more patients experience a DLT during the dose-escalation safety monitoring period of Part B (D1 to D22), then that dose level will be considered to have exceeded the NTD, and no further escalation will proceed.

The maximum tolerated dose (MTD) will be defined as the proximal dose level below the dose exceeding the NTD administered during the study. Of note, dose escalation may not identify an NTD or MTD.

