### **10.7.** ASSIGNMENT TO TREATMENT

Once a patient has met all entry criteria, he or she will be assigned a distinct patient identifier. If a patient discontinues from the study, the patient identifier will not be reused, and the patient will not be allowed to reenter the study.

In Part A, patients will be assigned to receive open-label ANK-700 at a dose level based on the next available spot in the cohort(s) currently being enrolled. Patients in Part A may be replaced if they do not receive the full dose of study drug or do not complete the D15 visit, as long as the discontinuation was not due to a DLT

In Part B, patients will be stratified based upon their use of fumarate at study entry within the IRT system. For the sentinel group, the first 2 eligible patients within each cohort will be randomized through IRT in a 1:1 ratio to receive either ANK-700 or PBO. After completion of the sentinel dosing in each cohort, the remaining 10 patients will be randomized to ensure an overall 2:1 randomization to ANK-700 and PBO. Patients in Part B may be replaced if they do not receive the full 3 doses of study drug or do not complete the D22 visit, as long as the discontinuation was not due to a DLT.

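### Part B has two release days for dosing after the sentinel pair, D21 and D22, and the D21 version allows the next patient to be dosed before the sentinels' only routine post-dose-3 labs and vital signs

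*Protocol*

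**What the plan says.** Part B gives three infusions, on D1, D4 and D7. The first two patients in each cohort are sentinels, and dosing of the remaining ten waits for them. The end of that wait is given differently:

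- Protocol 4.2: the sentinels must "complete an additional 14 days of safety monitoring (through D21) before initiating dosing for any subsequent patients". SAP 2.3.2 gives the same rule with the same end day.
- Protocol synopsis, Part B: they must "complete an additional 14 days of safety monitoring (through D22) before dosing can be initiated in any further patients".
- Protocol 10.7 gives no day: "After completion of the sentinel dosing in each cohort, the remaining 10 patients will be randomized". SAP 3.2.2 likewise gives none.

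Other Part B rules use D22. Protocol 4.7 defines the window: "The dose-escalation safety monitoring period in Part B is from the beginning of the first IV administration of ANK-700/PBO through the D22 clinic visit". For the next cohort, the Figure 1 text in Protocol 4.2 says "Initiation of Cohort 5 will commence once all patients in Cohort 4 reach D22".

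**The concern.** This rule releases further dosing in the first multiple-dose part of a first-in-human study, and sites hold two versions of it. The D21 version opens dosing on the calendar day of the later sentinel's D22 visit, and nothing says the visit must come first.

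That visit carries most of the planned safety information after dose 3. ANK-700 is designed to distribute to the liver (Protocol 1.2). A symptomless enzyme rise after the third dose would be found by a blood draw, and the first scheduled draw is on D22. A Grade 2 AE that has not resolved within 14 days is a DLT. For one starting on D7, the 14 days end on D21, so D22 is the first scheduled visit at which non-resolution can be confirmed.

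**Working it through.** **Inputs**

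- Third dose on D7 (Protocol 4.2).
- Day count: 14 days after a D1 dose is D15 (synopsis, Starting Dose and Dose Escalation), so the end day is dose day + 14.
- Part B visit days: 1, 4, 7, 22, 43, 90, 182 and 365 (Protocol Tables 2 and 3). D22 has no visit window.
- Labs on D7 carry footnote g: "Samples/measurements taken pre-dose".
- First randomization block of three, with two ANK-700 and one placebo and the first two treatments different; the two fumarate strata must have different orders (SAP 3.2.2).

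**The end day**

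- D7 + 14 = D21, so Protocol 4.2 and SAP 2.3.2 agree with their own 14 days.
- D22 − D7 = 15 days, so the synopsis does not agree with its own 14 days.
- The two rules differ by D22 − D21 = 1 day.

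| Rule | Earliest next first dose (later sentinel's day) | D22 visit inside the hold | Days of DLT window not covered |
|---|---|---|---|
| Through D21 | D22 | No | 22 − 21 = 1 |
| Through D22, read inclusively | D23 | Yes, if on time | 22 − 22 = 0 |

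**What falls on D22**

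- Safety labs: before dosing on D1, D4 and D7, then D22, with no later scheduled visit. The only other entry is an early-termination visit.
- Vital signs: before dosing on D1, then D22, with no later scheduled visit.
- EDSS: before dosing on D1, then D22, D90, D182 and D365.
- MRI: D22, but allowed up to 3 days earlier (D19 to D22). Of these four assessments, only the MRI can fall before D22.

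**Does another clause settle it?** No. Protocol 12 lets the final SAP prevail over the protocol, but for statistical methods. When to dose the next patient is not one.

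**How often the active sentinel is the later one**

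The first-block rules leave two orders: ANK-PBO-ANK and PBO-ANK-ANK. Assume that they are equally likely and that the sentinels are dosed on different days in randomization order. Neither assumption is stated in the documents.

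- Pair from one stratum: the second patient is on ANK-700 in one of the two orders, probability 1/2.
- Pair from two strata: one stratum starts with ANK-700 and the other with placebo, so the later patient is on ANK-700 with probability 1/2.
- At least one of the two cohorts, taken as independent: 1 − (1/2)² = 3/4.
- If both sentinels are dosed on the same day, the probability is 1.

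These figures describe the order of the sentinels. They are not a probability of harm.

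**Exposure of an early-dosed patient**

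A patient first dosed on the sentinel's D22 has had 1 of 3 doses, and the second is due 3 days later. A pause within those 3 days spares doses 2 and 3.

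**The case against.** The substance of the rule is the same everywhere: three doses, then 14 days of monitoring. Only the bracketed end day differs, by one day, and the slip is arguably in the synopsis. No version actually requires the D22 visit to be completed, so tying release to it adds a requirement. Part A also works by calendar gap: patients are dosed at least 14 days apart, which permits a next dose on the earlier patient's D15 visit day.

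There is further reassurance. Patients are observed for 4 hours after dose 3. Drug clears from circulation in under 7 minutes in animals, and active antigen is undetectable after 7 days. Cohort 4 gives 3 × 0.3 = 0.9 mg/kg in total and starts only after review of a 1.0 mg/kg single dose. A completed visit also secures only collection of the labs, not their review.

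Much of this stands, and it limits the weight of the point. Harm would need a patient dosed on exactly that day, before that day's visit, and an abnormality first seen at the visit. Visit completion is indeed a recommendation on how to resolve the conflict. But none of this says which day governs. Part A differs in having a scheduled lab draw on about D4, between dose and D15, whereas Part B has none between D7 and D22. Single-dose experience and clearance data do not replace the first scheduled look after three doses.

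**Conclusion.** The concern holds. The current text gives two end days for one dosing-release rule, and neither document resolves them. The gap is at most about one day if the D22 visit is on time.

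The consequence is limited. It arises mainly when the ANK-700 sentinel is the later one or both are dosed together; the 1/2 per cohort and 3/4 over two cohorts rest on the assumptions given with them. Few patients could be affected, and the documents do not allow a count. Protocol 4.6 adds a safeguard, "Any DLT experienced during the dose-escalation safety monitoring period will result in study pause and review by the SMC", and Protocol 4.9 says that after one DLT in Part B "the study will be paused to determine if any dose adjustments are needed and/or if the study should dose any additional patients". No endpoint or analysis set depends on the sentinel day. The plan should be corrected because this is a safety threshold, D22 is where the post-dose-3 information is collected, and the correction is cheap.

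**What to change.** In the synopsis, Protocol 4.2 and SAP 2.3.2, state that no further patient in the cohort is dosed until both sentinels have completed the D22 visit, which is 15 days after the third dose and the end of the DLT window. Replace the 14-day figure accordingly. The rule must name both sentinels, because blinded sites cannot tell which one received ANK-700. Refer to it from Protocol 10.7 and SAP 3.2.2.

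Two additions are optional. The sponsor could require review of the D22 local lab results before release. If a cohort has already been released, the sponsor should record which version was applied.

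The cost is about one day per cohort, a protocol wording amendment that goes to the IRB/IEC (Protocol 13.4), and matching edits to SAP 2.3.2 and 3.2.2.

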# **4.3. DOSING FREQUENCY**

In Part A, patients will receive a single IV infusion of ANK-700 on D1.

In Part B, patients will receive a total of 3 IV infusions of either ANK-700 or PBO (double-blind). A single IV infusion will be administered on D1, D4, and D7.

#### 4.4. BLINDING

Part A is open-label.

Part B is double-blinded, such that study personnel (e.g., investigators, site coordinators) and patients are blinded to treatment assignments and will remain blinded throughout the study.

Unblinded personnel include those involved in drug preparation and allocation (e.g., data systems support and pharmacists) and those involved in SMC data preparation, including the study pharmacokineticist, to allow for expedited review of PK data before SMC review.

The data reviewed for dose escalation in Part B will be presented and reviewed by the SMC in a blinded fashion.

Study ANK-700-01 in Relapsing-Remitting Multiple Sclerosis

If a medical emergency occurs, the site may be unblinded if knowledge of the study treatment is necessary to provide appropriate urgent medical care.

#### 4.5. MONITORING OF ADVERSE EVENTS

Patients will be monitored continuously for AEs while on study. AE severity will be assessed using the NCI-CTCAE v5.0 or higher (Appendix 1).

#### **4.6. DOSE-LIMITING TOXICITIES**

Dose-limiting toxicities for Study ANK-700-01 include any Grade 2 AE not resolving within 14 days or any ≥ Grade 3 AE occurring during the dose-escalation safety monitoring period (D1 to D15 in Part A; D1 to D22 in Part B). DLTs do not include those AEs attributable solely to intercurrent illness or other concomitant medications. Any DLT experienced during the dose-escalation safety monitoring period will result in study pause and review by the SMC.

Any  $\geq$  Grade 4 AE will result in notification to the Food and Drug Administration (FDA) in parallel with the SMC; all study dosing and enrollment will be paused pending review by FDA.

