#### **Starting Dose and Dose Escalation**

The starting dose of ANK-700 will be 0.3 mg/kg based on findings from Good Laboratory Practice (GLP) toxicology studies and animal models in MS, which identified the pharmacologically active doses.

Part A will employ a 3+3 design to evaluate single ascending doses of ANK-700. At any dose level, if none of the first 3 patients dosed experience a DLT within 14 days of treatment, then escalation to the next dose level may proceed if recommended by the SMC and approved by the Sponsor. If 1 of the first 3 patients in the cohort experiences a DLT within 14 days of treatment (D1 to D15), the dose level may expand to a maximum of 6 patients. If no DLT occurs among the additional patients enrolled at that dose level, then escalation to the next dose level may proceed if recommended by the SMC and approved by the Sponsor. The first

MAD cohort (Cohort 4) will be initiated after the safety review of SAD Cohort 2 (Part A), a recommendation to proceed by the SMC, and approval by the Sponsor. Cohort 5 will only commence after review of the safety, tolerability, and available PK data of all the SAD cohorts (Cohorts 1 to 3) and Cohort 4, recommendation by the SMC, and approval by the Sponsor.

DLTs include any Grade 2 AE not resolving within 14 days or any ≥ Grade 3 AE occurring during the dose-escalation safety monitoring period (D1 to D15 in Part A; D1 to D22 in Part B).

Any  $\geq$  Grade 4 AE will result in notification to the Food and Drug Administration (FDA) in parallel with the SMC; all study dosing and enrollment will be paused pending review by the FDA.

The non-tolerated dose (NTD) is the dose level at which > 1 patient experiences a DLT during the dose-escalation safety monitoring period (D1 to D15 in Part A; D1 to D22 in Part B). The maximum tolerated dose (MTD) will be defined as the proximal dose level below the NTD administered during the study. Of note, dose escalation may not identify an NTD or MTD.

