# 4.1. PART A – SINGLE ASCENDING DOSE

The SAD phase will include up to 3 cohorts with 3 patients each. Patients within each dose cohort will receive 1 dose of ANK-700 IV and will be monitored for up to 6 months. All patients in Part A will be dosed  $\geq$  14 days apart to monitor for acute and subacute reactions; this length of time is supported by nonclinical exposure data that suggest ANK-700 will have cleared > 5 half-lives and nonclinical animal model data demonstrating that the tolerance induction mechanism can develop and immunologically active peptide is cleared within 1 week from dosing (see Section 4.7 for more information).

Patients will arrive at the clinic on the morning of dosing (Day 1 [D1]) and will be monitored inclinic for 8 hours after completion of ANK-700 infusion for assessment of acute safety and PK blood sample collection. A follow up phone call 24 hours after dosing must be performed to ensure the patient did not experience any acute safety events after discharge.

- If patients are experiencing active AE(s) which require clinical monitoring at the end of the clinic/hospital unit monitoring period, they should not be discharged and followed up per PI assessment
- If feasible, patients should be advised to have someone stay with them after discharge until 24 hours have elapsed after study drug administration on D1.
- If patients do not live within 1-hour travel time of an emergency medical facility, they should remain in the clinic/hospital unit for the first 24 hours after study drug administration.
- Patients should be instructed not to drive themselves to seek emergency medical treatment at any time during the study.

Doses evaluated in Part A include 0.3 mg/kg (Cohort 1), 1.0 mg/kg (Cohort 2), and 3.0 mg/kg (Cohort 3). After all patients within a given dose cohort have been followed for ≥ 14 days post-dose, a safety review will be performed by the SMC to review all adverse events (AEs) and available clinical laboratory and PK data. Initiation of the next dose level will commence upon recommendation by the SMC and approval by the Sponsor.

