Part A will employ a 3+3 design to evaluate single ascending doses of ANK-700. At any dose level, if none of the first 3 patients dosed experience a dose-limiting toxicity (DLT) within the dose-escalation safety monitoring period (D1 to D15), then escalation to the next dose level may proceed if recommended by the SMC and approved by the Sponsor. If 1 of the first 3 patients in the cohort experiences a DLT within the dose-escalation safety monitoring period (D1 to D15), the dose level may expand to a maximum of 6 patients. If no DLT occurs among the 3 additional

Study ANK-700-01 in Relapsing-Remitting Multiple Sclerosis

patients enrolled at that dose level, then escalation to the next dose level may proceed if recommended by the SMC and approved by the Sponsor.

For all patients in Part A, the study will consist of a 28-day screening period, a single dose of ANK-700 administered on D1, and an 8-hour monitoring period in the clinic/hospital unit and a phone call 24 hours after dosing. Patients will return to the clinic on D4±1, D15, and D29±1. Additionally, patients will return to the clinic after 3 and 6 months for follow-up. Blood and serum samples will be collected for PK and anti-drug antibody (ADA) assessments during Part A. Patients in Part A may be replaced if they do not receive the full dose of study drug or do not complete the D15 visit, as long as the discontinuation was not due to a DLT. In the event that patients are unable to return to the clinic for protocol-specified visits, alternative methods for safety assessments and data collection may be employed to ensure the safety of the patients where appropriate.

Please see Table 1 for the complete schedule of assessments for Part A.

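### The earliest escalation and sentinel-release decisions can come before an open Grade 2 AE is known to be a DLT or not, and no rule says how it counts

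*Protocol*

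**What the plan says.** **Definition.** Protocol 4.6, repeated in SAP 6.1.6, counts as a DLT "any Grade 2 AE not resolving within 14 days", or any AE of Grade 3 or higher, in the monitoring period: D1 to D15 in Part A, D1 to D22 in Part B. AEs due solely to intercurrent illness or other concomitant medication are excluded. Neither document says when the 14 days start.

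**Part A.** Section 4.1 permits the cohort review once all patients "have been followed for ≥ 14 days post-dose, a safety review will be performed by the SMC". Patients are dosed at least "14 days apart to monitor for acute and subacute reactions". In the synopsis, escalation may proceed "if none of the first 3 patients dosed experience a DLT within 14 days of treatment", subject to SMC recommendation and Sponsor approval.

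**Part B.** Section 4.2 has the two sentinels "complete an additional 14 days of safety monitoring (through D21) before initiating dosing for any subsequent patients"; the synopsis puts this as an "additional 14 days of safety monitoring (through D22) before dosing can be initiated in any further patients". The Cohort 4 review may follow once all its patients have 21 days of follow-up.

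**Stopping rules (4.9).** Any DLT in the monitoring period pauses enrolment. Two or more at a dose level in that period stop escalation.

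**SMC (4.7).** The SMC uses the AEs seen in the period. AEs that meet the DLT criteria but arise after the Part A period may be considered when choosing Part B doses.

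**The concern.** A Grade 3 event is a DLT on the day it happens. A Grade 2 event becomes one only through persistence, and the persistence period in Part A is as long as the follow-up required before the decision. A Grade 2 AE that starts after D1 and is still open at D15 is therefore neither a DLT nor cleared, yet the 3+3, pause and two-DLT rules count only DLTs. Followed as written, they can register zero DLTs in a cohort with an open event that later meets the definition.

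It is also unclear whether such an event counts afterwards. The definition in 4.6 ties the AE to the window, which favours attribution by onset. The synopsis and 4.9 place the DLT itself in the window, which, taken literally, requires the 14 days to end there too. Two careful readers could classify the same event differently, and the SAP's DLT listing would inherit the disagreement.

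The timing matters because 4.7 cites tolerance induction from about 1 week after dosing. A Part A event starting then, at about D8, reaches 14 days at about D22, a week after the earliest review.

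**Working it through.** The plan gives no figure for this point; the check is day arithmetic. Assumption: the 14 days run from onset, so the 14-day point is onset day + 14, and an open event is pending if decision day − onset day < 14.

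**1. Pending onset days**
- Part A, D15: onset D1 gives 15 − 1 = 14 (settled); D2 gives 13 (pending). Pending: D2-D15, 14 of 15 days.
- Sentinels at D21: 21 − 8 = 13. Pending: D8-D21, 14 of 21 days.
- Sentinels at D22, and Cohort 4 patients who have just reached D22: 22 − 9 = 13. Pending: D9-D22, 14 of 22 days.

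These apply only to events still open; one that has resolved within 14 days is settled.

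**2. Who is affected in Part A.** When the third patient reaches D15, the 14-day spacing puts the second at D29 or later and the first at D43 or later. The latest in-window onset, D15, is settled by 15 + 14 = D29. Only the last-dosed patient can be pending at the escalation review.

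**3. Latest settling day.** Part A: D29. Part B: 21 + 14 = D35 or 22 + 14 = D36.

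**4. Literal reading (the full 14 days must fall inside the window).** Latest qualifying onset is 15 − 14 = D1 in Part A and 22 − 14 = D8 in Part B, one day after the third dose. Counting onset day as day 1 gives D2 and D9.

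**5. Higher-dose exposure while pending**
- Part A: the first patient at the next dose can start at the last patient's D15; the second cannot start before 15 + 14 = D29. So 1 patient.
- Cohort 5: the 2 sentinels (1 active) can start at the last Cohort 4 patient's D22. Their own D21/D22 falls on that patient's D42/D43, 6 or 7 days after D36. So 2 patients.

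**6. Same-dose exposure**
- Part A: the next patient, 1.
- After sentinel release: 8 − 1 = 7 ANK-700 and 4 − 1 = 3 placebo, 10 in all (Protocol 10.7). An open event in either sentinel matters, because the SMC reviews Part B blinded and the DLT definition is not limited to active drug.
- Enrolment pace is not stated. Assuming one start every 1, 2, 3 or 7 days, the starts falling within 14 days number 10, 7, 5 or 2.
- Average implied by the synopsis dates: October 2020 to September 2023 is 35 months. Less 12 months of Part B follow-up leaves 23 months, about 23 × 30.4 = 699 days. 699 / 42 ≈ 17 and 699 / 33 ≈ 21 days per start, so about 1 start in 14 days.

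**7. Total dose already reviewed.** Cohort 4: 3 × 0.3 = 0.9 mg/kg, after review of a single 1.0 mg/kg. Cohort 5: 3 × 1.0 = 3.0 mg/kg, after review of a single 3.0 mg/kg.

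**The case against.** The other side has several good points.

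- **The definition favours onset.** On that reading, an event that converts late is still an in-window DLT, triggers the pause and counts toward the limit of two. What remains is a delay of at most 14 days. The rival reading rests on looser phrasing and would nearly empty the Grade 2 criterion in Part A, which argues against it. This stands, but the looser phrasing is in the stopping rule itself, so it needs correcting.
- **The clock may not run from onset.** The windows also fit a count from the last dose (D1 + 14 = D15; D7 + 14 = D21), and an event open at D15 could then be classed. The text does not say this, and it would make a Grade 2 AE that began on D14 a DLT after one day.
- **The DLT count does not decide escalation alone.** The SMC uses all in-window AEs, 14 days is a minimum in Part A, and escalation is only permitted, never automatic. This stands: the event is visible and the SMC may wait. It still has no statement of whether the event counts toward a binding rule.
- **Section 4.7 covers late events.** It addresses AEs that arise after the Part A window, leaves them to discretion and has no Part B counterpart. It does not clearly reach an event that starts inside the window and matters 14 days later.
- **Exposure is small.** Spacing, sentinels and prior review of single doses at least as large as each Part B total all limit it. This stands.

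**Conclusion.** The point holds as a gap in the decision rules. At the earliest permitted decisions, an open Grade 2 AE less than 14 days old has no settled status, and neither document says whether it counts once it matures after the window. The affected onset days are D2-D15 in the last-dosed Part A patient, D8-D21 or D9-D22 in a sentinel, and D9-D22 in a late-enrolled Cohort 4 patient. This rests on a 14-day clock starting at onset, which is assumed, and shifts by a day with the counting convention. The Grade 3 or higher criterion is unaffected.

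Three stronger inferences are not supported. A reader might conclude that the plan would escalate past a real DLT; the SMC's full view of AEs and freedom to wait make that possible, not shown. A reader might conclude that the Grade 2 criterion is void in Part A; that follows only from the literal reading, and the definition favours the other. A reader might take 10 patients as the expected exposure after sentinel release; it is an upper bound for batched enrolment, against about 1 start at the average pace, and that average may not describe enrolment just after a gate opens.

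The change should be made: it settles a safety rule in a first-in-human trial at little cost.

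**What to change.** In Protocol 4.6 and 4.9 and SAP 6.1.6, state:

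1. The 14 days run from AE onset. DLT status is assigned by onset within D1-D15 (Part A) or D1-D22 (Part B), even if the 14 days end later. The pause and two-DLT rules apply when the event converts.
2. Cohort escalation and sentinel release wait until any open Grade 2 AE, unless solely attributable to intercurrent illness or concomitant medication, resolves or reaches 14 days: at the latest D29 in Part A and D35/D36 in Part B. The SMC package lists each open event with its onset day.

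No extra hold is proposed for the next patient at the same Part A dose.

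A phone contact 14 days after onset is optional. Part A has a visit at D29±1. In Part B, events pending at D22 mature on D23-D36 and the next visit is D43±2, 41 − 36 = 5 to 45 − 23 = 22 days later, but AEs are already monitored continuously and followed to resolution.

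The cost is wording in two documents, one SMC listing, and a delay of up to about 14 days only when such an event is open. The hold takes some discretion from the SMC and could be triggered by an event in a placebo sentinel.
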